5 INTERVENTIONS AND STUDY DEVICE

5.1 INTERVENTION

Patients in both treatment groups will be prescribed standard of care oral rehydration solution (ORS) treatment.

Patients will be randomised in 1:1 ratio using a computer-based stratified permuted blocks randomisation tool developed by Sealed Envelope Ltd (London, UK) to:

Control Group: will receive a prescription for standard of care ORS treatment **Interventional Group**: will receive a prescription for standard of care ORS treatment together with an intestinal adsorbent, over-the-counter medical device, Enterosgel® (Bioline Products s.r.o, Czech Republic) to be taken according to study-specific dosage instructions provided in **Appendix A** for 5-7 days. Patients will be given 2 tubes of Enterosgel® 225 g and a pack of 10 Enterosgel® sachets to provide a more convenient alternative if the patient is not at home.

Randomisation will be stratified by site identifier.

5.2 STUDY DEVICE

5.2.1 Description of study device

Enterosgel® is an over-the-counter intestinal adsorbent developed for binding toxins, harmful substances, pathogens and allergens in the gastrointestinal tract (**Appendix B**). It does not cross the intestinal barrier and is classified as a medical device. In Europe, it was certified as a medical device class IIA in 2008 with an indication for diarrhoea.

Enterosgel® is а polymethylsiloxane based hydrogel produced polycondensation of methylsilicic acid with the loss of water and formation of siloxane bonds (12). It is completely excreted and exhibits selective sorptive activity towards medium and high-molecular weight substances in the gut, including middle-molecular weight toxic metabolites. Because of the selective adsorption, Enterosgel® is believed not to adsorb medications. However, it is still recommended to leave at least one hour between taking Enterosgel® and other medications. It is free from preservatives, sugar and other additives and is considered to be non-allergenic. It is easily suspended in water and taken orally, and has no taste. Enterosgel® can be used in children and adults, including pregnant and breastfeeding women.

Enterosgel® is used in 30 countries, and in some of them for over 20 years, without reported adverse reactions. According to European database of suspected adverse drug reaction reports (http://www.adrreports.eu/en/index.html) there are no reported adverse reactions in Europe since it was certified in 2008. Enterosgel® is available from pharmacies and health stores in the UK in a form of gel and is available in a tube or in a packet of 10 sachets.

5.2.2 Labelling, storage and destruction

Study devices will be marked with a label containing the text "FOR RESEARCH PURPOSES" and the following fields:

- 1. Patient's name
- 2. Patient's Date of Birth
- 3. Study reference (i.e. ENT02UK)
- 4. Pl's name

Study devices will be stored at the medical practice in a secure, restricted access room under room temperature conditions. Dispensing of study devices will be recorded in a study dispensing log for device accountability. Unused devices will be returned to the Sponsor for destruction at the end of the study. As the device is an over-the-counter product, the patients can dispose of the empty tubes at home and keep any remaining unused Enterosgel®.

5.3 CONCOMITANT TREATMENTS

All patients will be prescribed standard of care ORS treatment throughout the study. Patients should not use any other diarrhoea medication, such as antidiarrhoeal treatments, during the study unless prescribed by their doctor. During the study the nurse will ask the patients about their diarrhoea medication use, and use of any other diarrhoea medication should be recorded in the eCRF. Any patients who have taken antidiarrhoeal medications (such as loperamide) will be excluded from the analyses.

If the GP decides to add antibiotic therapy, the details including the reason for antibiotic therapy will be recorded in the eCRF and source documents for both groups. Patients in the Interventional group will still take Enterosgel® along with the antibiotic therapy giving 1-2 hours between taking the antibiotic and Enterosgel®.

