6 STUDY SCHEDULE AND PROCEDURES

Patients will complete 1 visit at their GP practice with 7 follow-up phone calls after the visit. The patients will not be invited for visits outside their standard of care regime. The schedule of visits/calls, and the procedures conducted and data collected at each visit/call are presented in **Table 1**. A +/- 2-day deviation is allowed for the Day 7 follow-up call.

Table 1. Schedule of procedures and data collection.

Procedure	Day 0 (Screening Visit)	Days 1- 7 (Follow-up calls)	End of study
Patient screening and consent	Х		
Demographic information and relevant medical history, symptoms and medication	x		
Randomisation	X		
Prescription for ORS (all patients) and provision of Enterosgel® (Interventional group)	Х		
Stool sample	X		
Other symptoms (vomiting, abdominal pain, nausea, fever etc)*	х	х	
Body temperature*		x	
Stool frequency and form*		х	
Medication use*		х	
Adverse Events*	 	x	
Returning of the diaries			х

^{*}Recorded by the patient in a patient diary from Day 0 (after randomisation) until end of Day 7 (**Appendix C**)

6.1.1 Day 0

On the Day 0 appointment, the patient's eligibility to take part in the study will be confirmed by the GP and written informed consent will be obtained by the GP or nurse before any study procedures take place. Screening will include a physical examination by the GP/nurse to ensure the patient is suitable to take part in the study (including measurement of body temperature, pulse and blood pressure).

The following information is then recorded in the eCRF:

- 1. Demographic information (age, gender, ethnicity)
- 2. Relevant medical history:
 - a) date of onset of symptoms (diarrhoea, vomiting, nausea, abdominal pain, fever etc.)
 - b) contact with suspected infection
 - c) details of travel
 - d) details of possible food poisoning
 - e) any antidiarrheal medication taken during the current episode

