8.2 STATISTICAL ANALYSES

A CONSORT flow diagram will show the progress through the parallel randomised trial (that is, enrollment, intervention allocation, follow-up, and data analysis). The baseline characteristics of the groups will be summarised as mean (standard deviation) or n (%). The baseline characteristics will not be compared statistically, in line with CONSORT.

Primary analysis will be conducted on an intention-to-treat basis. The primary outcome will be summarised as mean (standard deviation). The Interventional

group and Control group will be compared using a t-test or Mann Whitney test, as appropriate. A generalised linear model will undertaken to control for an potentially confounding variables, e.g. age and gender.

Secondary outcomes will be summarised as mean (standard deviation) or n(%) median (interquartile range). The Interventional group and Control group will be compared using a t-test or Mann Whitney test for continuous data (e.g. duration of nausea, vomiting and fever) and chi-square tests for categorical data (e.g. complication rate).

A p-value of <0.05 will be considered to indicate statistical significance and all analyses will be undertaken on STATA.

A 30% drop out has been taken into account in the sample size calculation for the primary analysis to allow for missing data. The extent and reasons for missing data will be reported and investigated to see whether the data is missing at random. This will inform which methods to handle missing data will be employed. Sensitivity analyses will be performed as appropriate.

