8.3 ANALYSIS POPULATIONS

8.3.1 Intention-to-treat population (ITT)

ITT population will include all randomised patients analysed in the groups to which they were randomised to, regardless of whether they received or adhered to the allocated intervention.

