9.3 PROTOCOL DEVIATIONS AND VIOLATIONS

A protocol deviation is any noncompliance with the clinical trial protocol or GCP. The noncompliance may be either on the part of the participant, the investigator, or the study site staff.

Protocol violations are significant deviations that reduce the quality or completeness of the data, make the Informed Consent Form inaccurate, or impact a subject's safety, rights, or welfare (16).

Examples of protocol violations relevant to this study may include the following:

- 1. Inadequate or delinquent informed consent
- 2. Inclusion/exclusion criteria not met
- 3. Unreported SAEs
- 4. Use of any prohibited medication (i.e. any antidiarrhoeal medications)

- Inadequate completion of the patient diary (i.e. data missing systematically, diary missing entirely for one or more days, any data entry issues that compromise the verification of primary outcome data against the source)
- 6. Materially inadequate record keeping
- 7. Intentional deviation from the protocol, GCP, or regulations by study personnel
- 8. Subject repeated non-compliance with study requirements, including not using any Enterosgel®, if randomised to Enterosgel group

Examples of protocol deviations relevant to this study may include the following:

- 1. Stool sample not taken, or taken after Day 0
- 2. One or more calls missed
- Infrequent missing data in patient diary (however, any missing data affecting the interpretation of the primary outcome would be recorded as a protocol violation)

All deviations/violations must be addressed in study source documents and reported to the Sponsor and Research Ethics Committee (REC) and/or local authorities as per their guidelines. The site PI/study staff is responsible for knowing and adhering to these requirements. As a result of deviations and violations, corrective actions are to be developed by the Sponsor and/or site as appropriate and implemented promptly.

Patients with protocol violations will be excluded from the PP population.

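### Section 5.3 drops antidiarrhoeal users from the analyses without naming a population, contradicting the ITT primary analysis and the PP-only consequence in section 9.3

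*Protocol*

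**What the plan says.** - **Section 5.3** asks patients not to use other diarrhoea medication, "such as antidiarrhoeal treatments, during the study unless prescribed by their doctor". It has the nurse record any use in the eCRF, and then states: "Any patients who have taken antidiarrhoeal medications (such as loperamide) will be excluded from the analyses".
- **Section 8.2:** "Primary analysis will be conducted on an intention-to-treat basis".
- **Section 8.3.1:** "ITT population will include all randomised patients analysed in the groups to which they were randomised to", whatever treatment they took or kept to. No exception is made for concomitant medication.
- **Section 8.3.3** defines the safety population by receipt of at least one dose, also without such an exception.
- **Section 9.3** lists among its examples of violations "Use of any prohibited medication (i.e. any antidiarrhoeal medications"), and closes: "Patients with protocol violations will be excluded from the PP population". It states no other consequence for the analysis.
- **Section 6.1.1** records at Day 0 "any antidiarrheal medication taken during the current episode". Section 4.2 excludes patients who used antibiotics since onset, but not patients who used antidiarrhoeals.

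**The concern.** A patient who takes loperamide on Day 2 is in the primary analysis under 8.2, 8.3.1 and 9.3, and out of it under 5.3. The membership of the primary population is therefore not fixed, and someone could settle it after seeing unblinded data. Section 5.3 also conflicts with itself, because a patient given an antidiarrhoeal by the doctor has followed the protocol and is still dropped.

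The literal 5.3 rule is the harmful one. The primary outcome (3.2.1) is the time from randomisation to the first non-watery stool. Antidiarrhoeal use after randomisation is plausibly more likely the longer the diarrhoea lasts, so dropping users would tend to drop slow recoverers. Participants know their allocation (3.1) and controls receive ORS alone (5.1), so use may differ between arms. Excluding patients on such an event gives up the protection of randomisation. Read literally, 5.3 would also drop users' adverse events from the safety summary.

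**Working it through.** **1. The contradiction.** This step needs no arithmetic.

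| Section | Antidiarrhoeal user in ITT? | In PP? | In safety? |
|---|---|---|---|
| 5.3, literal | no | no | no |
| 8.2 with 8.3.1 | yes | – | – |
| 8.3.3 | – | – | yes, if dosed |
| 9.3 | not removed | no | not removed |

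The sections agree on PP only.

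**2. The plan's own sample size (8.1).** Inputs: difference 1 day, SD 1.3 days, 5% level (two-sided), 90% power.
- n per group = 2 × [1.3 × (1.960 + 1.282)]² / 1² = 35.5, rounded up to 36.
- 36 / 0.70 = 51.4, rounded up to 52; total 104.

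Both stated figures reproduce. A one-sided 5% test would need 29 per group.

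**3. Size of the bias with no true effect.** The protocol gives neither use rates nor a mean duration. Assumptions: gamma durations with mean 3 days; SD 1.3 (from 8.1) or 2.0 (assumed); a constant daily chance h of starting an antidiarrhoeal while ill; every user dropped.

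A patient with duration D is kept with probability (1 − h)^D = exp(−λD), where λ = −ln(1 − h). The kept durations are again gamma, with mean k / (r + λ), where k = mean²/SD² and r = mean/SD².
- SD 1.3: k = 9/1.69 = 5.325, r = 3/1.69 = 1.775.
- SD 2.0: k = 9/4 = 2.25, r = 3/4 = 0.75.
- λ is 0.1054 at 10%, 0.0305 at 3%, 0.0513 at 5% and 0.0202 at 2%.

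| Control v Enterosgel use per ill day | SD | Kept mean, control | Kept mean, Enterosgel | Spurious difference |
|---|---|---|---|---|
| 10% v 3% | 1.3 | 2.83 | 2.95 | 0.12 day |
| 10% v 3% | 2.0 | 2.63 | 2.88 | 0.25 day |
| 5% v 2% | 1.3 | 2.92 | 2.97 | 0.05 day |
| 5% v 2% | 2.0 | 2.81 | 2.92 | 0.11 day |

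In all four rows the difference is against Enterosgel. Swapping the rates reverses the sign, and equal rates give zero. Simulation counting whole ill days agrees: about 0.11 to 0.26 day at 10% v 3%, with about 22% and 7% of patients dropped.

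**4. Type I error, simulated under the same assumptions.**
- 10% v 3%, 52 per arm: two-sided rejection 8.1% (SD 1.3) to 9.5% (SD 2.0). Of this, 7.4 and 8.9 percentage points are findings against Enterosgel. False findings of benefit fall to about 0.6–0.7%, below the nominal 2.5%.
- The same rates at 36 per arm: 6.4% to 7.7%.
- 5% v 2%, 52 per arm: 4.9% to 5.4%.
- 3% v 10% (heavier Enterosgel use): false findings of benefit rise to about 6–8%.

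**5. With a true 1-day benefit.** This uses a different assumed mechanism: a share of patients still ill beyond the control mean (3 days) is dropped, with SD 1.3 and 36 per arm before exclusion. Simulated power without exclusions is 89%.

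| Share dropped, control v Enterosgel | Estimated benefit | Power |
|---|---|---|
| 25% v 25% | 0.96 day | 86% |
| 50% v 50% | 0.89 day | 84% |
| 50% v 25% | 0.78 day | 70% |
| 25% v 50% | 1.08 day | 94% |

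When there is a real effect, equal use is not quite neutral, because the control arm has more slow recoverers to lose. The 94% in the last row reflects an inflated estimate.

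**The case against.** The best defence is that 5.3 is loose shorthand for the PP rule. The sections that deal with analysis (8.2, 8.3.1, 9.3) agree with one another, and a reader who gives them priority reaches the right population. That stands as a likely intention. But the sentence names no population, and 9.3 already covers PP, so the conflict remains for whoever applies 5.3 as written. Equally, one should not infer that the plan as a whole has decided to drop users from ITT; it gives two incompatible instructions.

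Three further inferences are tempting and are not supported:

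- **That the rule inflates type I error to 8–10% in general.** This comes from one assumed scenario at 52 per arm, and there nearly all the excess is against Enterosgel. At 5% v 2% the error is near nominal. The protocol documents no use rate, and it restricts non-prescribed use.
- **That these exclusions add to the 30% loss in 8.1.** Section 4.4 withdraws patients for major violations that affect data quality, so some users may already be counted in the 30%. If all came on top, 22% and 7% would leave 36.4 × 0.78 = 28.4 and 36.4 × 0.93 = 33.9 patients (36.4 = 52 × 0.70), and t-test power would fall from 89.6% to 84.5%. That is an outer case.
- **That use before randomisation is clearly caught.** The wording allows this reading, and 6.1.1 collects the information, but the preceding sentences of 5.3 concern use during the study. Excluding on a baseline fact would cost patients without creating the post-randomisation bias described here. It needs a clarifying clause and is secondary.

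**Conclusion.** The contradiction is certain and rests on the text alone: 5.3 cannot be applied together with 8.2, 8.3.1 and 9.3, and its literal form is unsuitable for the primary analysis.

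The bias is conditional. It needs antidiarrhoeal use that depends on continuing diarrhoea and, when there is no true effect, use that differs by arm. Under the assumed rates it is about 0.05 to 0.25 day, against a planned effect of 1 day. It is about zero with equal use and no true effect. Its direction is not fixed, so the documents do not support saying that the rule favours Enterosgel or that it works against it. That uncertainty is itself a reason to settle the population before any data are seen.

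**What to change.** **Replace the 5.3 sentence** with wording such as: *Patients who take antidiarrhoeal medication stay in the ITT primary analysis and the safety population and are left out of the PP population only (9.3).* State that this covers prescribed use and use before randomisation. This concerns analysis sets only; no view is taken on whether antidiarrhoeals should be permitted.

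**Reconcile with section 4.4.** Data collection stops when a patient is withdrawn, and a major protocol violation is a ground for withdrawal. If antidiarrhoeal use were treated as such a violation, users kept in ITT would have no outcome after that point. The sections should make clear that antidiarrhoeal use alone does not end the diary collection needed for the ITT outcome.

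**Optional sensitivity analysis.** Treat users as unresolved from the calendar day of first recorded use. The day has to serve because the diary (Appendix C) asks about other diarrhoea medication per day and requests no clock time. Assigning the worst rank fits the Mann-Whitney comparison already in 8.2; censoring would need a time-to-event method that 8.2 does not name. This analysis is useful because ITT includes whatever effect the antidiarrhoeal itself has on stool form.

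**Cost.** One replaced sentence with its clarification, one cross-reference to 4.4, and at most one extra analysis. Use by day is already recorded. The sample size stays at 36 evaluable and 52 randomised per group, 104 in total.

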6 STUDY SCHEDULE AND PROCEDURES

Patients will complete 1 visit at their GP practice with 7 follow-up phone calls after the visit. The patients will not be invited for visits outside their standard of care regime. The schedule of visits/calls, and the procedures conducted and data collected at each visit/call are presented in **Table 1**. A +/- 2-day deviation is allowed for the Day 7 follow-up call.

Table 1. Schedule of procedures and data collection.

Procedure	Day 0 (Screening Visit)	Days 1- 7 (Follow-up calls)	End of study
Patient screening and consent	Х		
Demographic information and relevant medical history, symptoms and medication	x		
Randomisation	X		
Prescription for ORS (all patients) and provision of Enterosgel® (Interventional group)	Х		
Stool sample	X		
Other symptoms (vomiting, abdominal pain, nausea, fever etc)*	х	х	
Body temperature*		x	
Stool frequency and form*		х	
Medication use*		х	
Adverse Events*	 	x	
Returning of the diaries			х

^{*}Recorded by the patient in a patient diary from Day 0 (after randomisation) until end of Day 7 (**Appendix C**)

6.1.1 Day 0

On the Day 0 appointment, the patient's eligibility to take part in the study will be confirmed by the GP and written informed consent will be obtained by the GP or nurse before any study procedures take place. Screening will include a physical examination by the GP/nurse to ensure the patient is suitable to take part in the study (including measurement of body temperature, pulse and blood pressure).

The following information is then recorded in the eCRF:

- 1. Demographic information (age, gender, ethnicity)
- 2. Relevant medical history:
 - a) date of onset of symptoms (diarrhoea, vomiting, nausea, abdominal pain, fever etc.)
 - b) contact with suspected infection
 - c) details of travel
 - d) details of possible food poisoning
 - e) any antidiarrheal medication taken during the current episode

The research nurse or GP will then randomise the patient to the intervention group using a computerised randomisation tool. Patients randomised to the Interventional group will be provided with a sufficient amount of Enterosgel® for 5-7 days of treatment and should take Enterosgel® as instructed in the study-specific instructions which will be provided to them (**Appendix A**). Patients randomised to the Control group will not receive any treatment in addition to the standard of care ORS treatment. The details of prescribed ORS treatment and any dietary recommendations will be recorded in the eCRF.

All patients will be provided with a patient diary (**Appendix C**) to record:

- 1. stool times and consistency
- 2. diarrhoea medication use
- 3. other symptoms (fever, nausea, vomiting etc.)
- 4. any AEs

Patients should fill in the patient diary daily from Day 0 until end of Day 7.

Patients will be asked to take a stool sample on the same day at home in a provided clean container. Patients in the Interventional Group should take the stool sample before taking the first Enterosgel® dose. ORS treatment can be started before taking the stool sample. The sample should be taken to the medical practice by the patient or a family member/friend. It will then be delivered to a local laboratory to test for the presence of rotavirus and diarrhoea causing bacteria (i.e.

Campylobacter, Clostridium difficile, Escherichia coli, Salmonella enterica, Shigella), in order to identify the likely cause of the episode. If there is a reason to suspect norovirus infection (i.e. outbreak), this will also be tested for. Patients who have recently travelled abroad will be additionally tested for *Pseudomonas* and *Vibrio cholerae*. A stool sample will only be collected in baseline and the results will be summarised in baseline characteristics.

6.1.2 Days 1-7

During the study, the patients will fill the patient diary (**Appendix C**) from Day 0 (after randomisation) until end of Day 7, measure their body temperature twice a day, and take ORS as prescribed and ® according to study-specific instructions provided in **Appendix A**.

Every morning between 8 am to 11am, the research nurse will call the patients to ask about the information recorded in the patient diary and record it in the eCRF. On Day 7, the patients should continue to fill the diary after the call until end of the day. After completing the study, the patients should return the patient diaries to the medical practice. A pre-paid envelope will be provided.

6.1.3 Unscheduled visits

Any unscheduled visits to the medical practice, home visits by nurse/GP, hospitalisations or visits to the Accident & Emergency department due to diarrhoea or related symptoms or due to AEs will be recorded in the eCRF and the source documents.

7 SAFETY

7.1 DEFINITIONS

Types of AEs associated with medical devices and applicable for this study are defined in accordance with the European Commission guidelines on medical devices (13).

Adverse Event (AE)

Any untoward medical occurrence, unintended disease or injury or any untoward clinical signs (including an abnormal laboratory finding) in subjects, users or other persons whether or not related to the investigational medical device.

NOTE 1: This includes events related to the investigational device or the comparator.

NOTE 2: This includes events related to the procedures involved (any procedure in the clinical investigation plan).

NOTE 3: For users or other persons this is restricted to events related to the investigational medical device.

ENT02UK Protocol v.1.4 11/06/2018

Adverse Device Effect (ADE)

AE related to the use of an investigational medical device.

NOTE 1: This includes any AE resulting from insufficiencies or inadequacies in the instructions for use, the deployment, the implantation, the installation, the operation, or any malfunction of the investigational medical device.

NOTE 2: This includes any event that is a result of a use error or intentional misuse.

Serious Adverse Device Effect (SADE)

Adverse device effect that has resulted in any of the consequences characteristic of a serious AE.

Serious Adverse Event (SAE)

AE that:

- a) led to a death,
- b) led to a serious deterioration in health that either:
 - 1. resulted in a life-threatening illness or injury, or
 - 2. resulted in a permanent impairment of a body structure or a body function, or
 - 3. required in-patient hospitalisation or prolongation of existing hospitalisation, or
 - 4. resulted in medical or surgical intervention to prevent life threatening illness or injury or permanent impairment to a body structure or a body function.
- c) led to fetal distress, fetal death or a congenital abnormality or birth defect.

NOTE 1: This includes device deficiencies that might have led to a SAE if a) suitable action had not been taken or b) intervention had not been made or c) if circumstances had been less fortunate. These are handled under the SAE reporting system.

NOTE 2: A planned hospitalisation for pre-existing condition, or a procedure required by the Clinical Investigation Plan, without a serious deterioration in health, is not considered to be a SAE.

Unanticipated Serious Adverse Device Effect (USADE)

Serious adverse device effect which by its nature, incidence, severity or outcome has not been identified in the current version of the risk analysis report. NOTE: Anticipated: an effect which by its nature, incidence, severity or outcome has been previously identified in the risk analysis report

